**Footnotes for Table 1:**

- a. Subjects who terminate the study prior to the Week 48 (end of study) visit should undergo all procedures noted for the early termination visit.
- b. Vital signs will include pulse rate, respiratory rate, body temperature, and systolic and diastolic blood pressure (average of 3 readings will be taken in a resting state).
- c. Anterior and posterior segments ocular examination, including dilated ophthalmoscopy, IOP, and slit lamp biomicroscopy (see [Appendix 2](#)).
- d. Check central retinal artery perfusion following study injection.
- e. At Day 1: measure IOP at 10 (+/- 5) and 60 (+/- 10) minutes following the EYP-1901 dose/sham injection. If IOP measurements at any study time points are 30 mmHg or higher, two additional measurements should be performed and IOP recorded as a mean of three measurements.
- f. All CFP images will be assessed by the CRC to determine the ETDRS-DRSS scores.
- g. Spectral-domain – optical coherence tomography angiography (SD-OCTA) or swept-source – optical coherence tomography angiography (SS-OCTA) imaging to be collected at these time points at pre-specified study sites where SD-OCTA equipment is available.
- h. Clinical laboratory testing will include HbA1c, hematology, serum chemistry, coagulation, and urinalysis evaluations (refer to the study Laboratory Manual).
- i. Documented HbA1c test results dated 60 days prior to the Screening Visit will be accepted.
- j. Females of childbearing potential only. Positive urine pregnancy results will be confirmed by a serum pregnancy test.
- k. Pharmacokinetic analyses of vorolanib and X-297, its main metabolite, will be performed on blood plasma samples.

This document is confidential.

## **5. Endpoints**

### **5.1. Primary Efficacy Endpoint**

The primary efficacy endpoint is the percentage of subjects improving  $\geq 2$  steps from baseline in the DRSS score in the study eye at Week 36 in each EYP-1901 dose level versus the sham IVT injection group.

### **5.2. Secondary Efficacy Endpoints**

The secondary objectives will be assessed with the following secondary endpoints in each EYP-1901 dose level versus the sham IVT injection group:

- Percentage of subjects improving  $\geq 2$  steps from baseline in the DRSS score in the study eye at Weeks 24 and 48 in each EYP-1901 dose level versus the sham IVT injection group.
- Percentage of subjects improving  $\geq 2$  steps or  $\geq 3$  steps over time in DRSS score in the study eye from baseline.
- Percentage of subjects worsening  $\geq 2$  steps or  $\geq 3$  steps over time in DRSS score in the study eye from baseline.
- Percentage of subjects who developed a vision-threatening complication due to diabetic retinopathy in the study eye at Weeks 24, 36, and 48.
- Percentage of subjects who developed CI-DME in the study eye at Weeks 24, 36, and 48.
- Time to develop any neovascular vision threatening complication (PDR/ASNV) in the study eye through Weeks 24, 36, and 48.
- Time to develop CI-DME in the study eye through Weeks 24, 36, and 48.
- Percentage of subjects who received anti-VEGF or additional standard of care intervention due to ocular diabetic complications in the study eye at Weeks 24, 36, and 48.
- Percentage of subjects who received PRP in the study eye, inclusive of subjects undergoing vitrectomy with endolaser, at Weeks 24, 36, and 48.
- Area under the curve (AUC) for change from baseline in BCVA in the study eye at Weeks 24, 36, and 48.

### **5.3. Pharmacokinetic Endpoints**

The PK endpoints are systemic exposure to vorolanib and X-297, its main metabolite, measured through plasma levels up to Weeks 24, 36, and 48.

### **5.4. Safety Endpoints**

The safety endpoints are the rates of ocular (study eye and non-study eye) and non-ocular TEAEs at Weeks 24, 36, and 48.

This document is confidential.

## **6. Analysis Sets**

### **6.1. Screened Set**

The Screened Set will include all subjects screened (who have signed informed consent).

### **6.2. Full Analysis Set**

The Full Analysis Set (FAS) will include all subjects who received study treatment (EYP-1901 or sham). Subjects will be assigned according to the treatment to which they were randomized. FAS will be used to summarize efficacy, demographic, and baseline data.

### **6.3. Per Protocol Set**

The Per-protocol (PP) Set will include all subjects who received study treatment (EYP-1901 or sham), continue until at least Week 36 (i.e., have had the primary endpoint assessed), and have no major protocol deviation(s) that would significantly impact the primary endpoint. Subjects will be assigned according to the treatment actually received. PP will be used to summarize the primary efficacy endpoint as sensitivity analysis.

### **6.4. Safety Set**

The Safety Set will include all subjects who received study treatment (EYP-1901 or sham). Subjects will be assigned according to treatment actually received. The Safety Set will be used to summarize treatment exposure and safety data.

### **6.5. Pharmacokinetic Set**

The PK Set will include all subjects in the Safety Set for whom at least 1 evaluable PK sample is available.

This document is confidential.

## **7. Estimands**

No estimands were defined within the protocol of this study.

This document is confidential.

## 8. General Aspects for Statistical Analysis

### 8.1. General Methods

- All analysis and summary outputs will be generated using SAS® version 9.4 or higher.
- Ocular data for both eyes are collected for each subject, but only 1 eye is identified as the study eye. Details regarding the presentation of individual analyses, that is, for study eye, non-study eye, or non-ocular, will be described in the relevant sections of this SAP as applicable.
- Continuous variables will be summarized using the number of subjects (n), mean, median, standard deviation (SD), minimum (min), and maximum (max).
- Categorical variables will be summarized using n and percentages of subjects.
- Time to event variables will be summarized using number and percentage of subjects with the event and censored and estimates of percentiles.
- All screened subjects will be included in subject data listings. Listings will be sorted by treatment arm, site, subject number, and date and time of assessment.
- Unscheduled visit data will be listed but not included in the by-visit summary tables, unless otherwise selected for analysis after application of visit windows (see [Section 8.4](#)).

### 8.2. Key Definitions

Baseline measurements are defined as the last non-missing measure prior to the initiation of study treatment, likely assessed at Screening or Day 1, but available unscheduled assessments will also be considered.

Study Day 1 will be the date on which study treatment is administered. Positive study days will be counted forward from Study Day 1, and negative study days will be counted backward from Study Day 1, beginning with Study Day -1. There will be no Study Day 0.

### 8.3. Missing Data

In general, missing data will not be imputed, unless otherwise specified. Every effort will be made to ensure completeness of data collection.

#### 8.3.1. Medication Dates

A partial/missing start date recorded on the Prior and Concomitant Medications case report form (CRF) will be handled as follows:

- If only the day is missing, and the month and year match the month and year of study drug administration date, then the day of the study drug administration date will be imputed. Otherwise, the first of the month will be used.
- If both the day and month are missing, and the year matches the year of the study drug administration date, then the month and the day of the study drug administration date will be imputed. Otherwise, 01 January will be used.
- If the start date is completely missing, the study drug administration date will be imputed, unless the stop date is prior to the study drug administration date, then the stop date of the medication will be imputed and the medication will be considered to be a prior medication.

This document is confidential.

A partial/missing end date recorded on the Prior and Concomitant Medications CRF will be handled as follows:

- If only the day is missing, then the last day of the month will be imputed.
- If both the day and month are missing, then 31 December will be imputed.
- If the stop date is completely missing, or if the medication is ongoing, then the study completion or discontinuation date will be used.

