7.5 Concomitant Medication Use

During the study, treatment for the progression of NPDR may be required in the study eye for some subjects as a result of AEs or lack of efficacy of the study treatment. Intervention per the clinical sites standard of care are permitted ([Section 6.6.4](#)). Prohibited medications ([Section 6.6.3](#)), although discouraged, can be used if necessary (eg, no other alternative) but will be considered protocol deviations. Information regarding concomitant medication use will be collected at the visits specified in [Table 5–1](#).

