## **9.5. Prior and Concomitant Medications**

Medications will be coded using the most recent version of the World Health Organization Drug Dictionary (Global B3 September 2021 Version). Missing medication dates will be handled as described in [Section 8.3.1](#). Anti-VEGF medications will be identified via review of standardized medication terms and flagged in the data.

Start date and stop date for medications, in conjunction with the ongoing indicator, from the eCRF will be used to determine whether medication is prior or concomitant.

Prior medication will be defined as all medications recorded on the “Concomitant Medication” CRF taken prior to study drug administration, whether continuing or not.

Concomitant medications will be defined as medications that are ongoing at study treatment administration or started on or after study treatment administration.

The number and percentage of subjects by treatment arm and overall in the Safety Set for prior medication (ocular study-eye, ocular non-study eye, and non-ocular summarized separately) and concomitant medication (ocular study eye, ocular non-study eye, and non-ocular summarized separately) will be summarized by Anatomical Therapeutic Chemical (ATC) level 2 and PT. They will be presented by descending overall count of ATC and within each ATC, by descending overall count of PT. Subjects will be counted only once for each ATC and PT if they have multiple records of the same ATC or PT in the database.

Prior to database lock, the sponsor will conduct a masked data review of medications to determine if any are classified as prohibited medications per the protocol; prohibited medications (if any) will be flagged in the prior and concomitant medication listings.

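### SAP 8.3.1 imputes partial medication start dates to the dosing date without checking the stop date, so a drug stopped before dosing can meet the definition of concomitant

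*SAP*

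**What the plan says.** SAP 8.3.1 has three rules for an incomplete medication start date.

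- **Day missing.** If the month and year are those of dosing, "then the day of the study drug administration date will be imputed". Otherwise the first of the month is used.
- **Day and month missing.** If the year is that of dosing, "then the month and the day of the study drug administration date will be imputed". Otherwise 01 January is used.
- **Completely missing.** The dosing date is used, "unless the stop date is prior to the study drug administration date, then the stop date of the medication will be imputed". In that case "the medication will be considered to be a prior medication".

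SAP 9.5 sends missing medication dates to these rules. It defines concomitant medications as "medications that are ongoing at study treatment administration or started on or after study treatment administration" and prior medications as those "taken prior to study drug administration, whether continuing or not".

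**The concern.** Only the third rule asks whether the drug had already stopped. Under the first two, a drug with a known stop before dosing is given a start on the dosing date, so it begins after it ended. A record that carries a partial start date is then handled worse than the same record with no start date at all.

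The omission looks unintended. The third rule contains the check, and the adverse event rule in SAP 8.3.2 looks at the end date first: an event that ended before treatment is not treatment-emergent, whatever its start date.

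At stake is the accuracy of the prior medication tables (14.1.4.1.1 to 14.1.4.1.3) and the concomitant medication tables (14.1.4.2.1 to 14.1.4.2.3). A course finished before dosing could be shown as on-study use.

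**Working it through.** The plan states no figure to reproduce. The check applies the three rules to one illustrative record and then asks whether the result is general.

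**Inputs**
- Imputation rules: SAP 8.3.1.
- Definitions of prior and concomitant: SAP 9.5.
- Collection window: Protocol 6.6.1 records medications taken in the 30 days before Day 1, whether or not they continue. Drugs already stopped are therefore on the form.
- Illustrative dates (assumed): dosing 20 May 2023, recorded stop 05 May 2023.

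**One record under the three rules**

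| Start as recorded | Imputed start | Imputed start minus stop | Starts on or after dosing? |
|---|---|---|---|
| May 2023, day unknown | 20 May 2023 | 20 − 5 = 15 days | Yes |
| 2023, day and month unknown | 20 May 2023 | 20 − 5 = 15 days | Yes |
| Nothing recorded | 05 May 2023 (the stop) | 0 days | No; prior by rule |

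**General result.** When either partial rule takes its dosing-date branch, imputed start = dosing date. If the recorded stop is before dosing, then stop < dosing date = imputed start. The inversion follows for every such record, and the imputed start always meets the second limb of the concomitant definition.

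Enumeration agrees. It took every dosing date in 2023 (an assumed year) and every start and stop pair in the 30 days before dosing:

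- Day missing in the dosing month: 56,354 of 56,354 combinations have start after stop.
- Day and month missing in the dosing year: 160,270 of 160,270.
- Start completely missing: 0 of 169,725.

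These are date combinations, not expected numbers of patients.

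**Where the problem stops.** If the partial start lies in an earlier month than dosing, the first of that month is imputed and nothing goes wrong. For example, with dosing 20 March 2023, start February 2023 and stop 10 March 2023, the imputed start is 01 February 2023. The drug is then prior and not concomitant.

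**Effect of the correction.** Imputing the stop date in both partial rules, as the third rule does, leaves 0 of 56,354 and 0 of 160,270 inversions. Imputing the first of the known month, or 01 January, also works: a drug cannot stop before the month or year in which it started, so the imputed start is never later than the stop.

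**Size in a table.** Arms have about 20 subjects. One wrongly placed subject changes a row of a medication table by 1/20 = 5 percentage points, unless that subject has another record of the same term that belongs there.

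**The case against.** The strongest reply is that SAP 9.5 does not classify on the imputed start alone. It says "Start date and stop date for medications, in conjunction with the ongoing indicator, from the eCRF will be used" to decide whether a drug is prior or concomitant, so a known stop before dosing is a stated input and a careful programmer could let it govern. The definition of prior also turns on when the drug was taken, not on an imputed start, so a drug stopped before dosing still fits it.

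This part stands. It would go too far to infer that every affected record must be misclassified, or that such a drug ceases to be prior. On the text, the record can meet both definitions, and the SAP does not say which date governs when an imputed start and a recorded stop conflict. That does not rescue the imputation rule: it still produces an impossible pair of dates, and the SAP writes the override only for completely missing starts.

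A second reply is that imputing the dosing date is the cautious choice. That is fair when the timing is unknown. Here the recorded stop settles it.

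A reader might also infer a path to the Per Protocol Set. Protocol 7.5 says that prohibited medications "can be used if necessary (eg, no other alternative) but will be considered protocol deviations", so a false start on Day 1 might look like on-study prohibited use. The documents do not support that chain:

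- Prohibited medications are identified by a masked sponsor review (SAP 9.5), and nothing suggests that reviewers would ignore a recorded stop.
- Deviations are collected by monitors in the trial management system (SAP 9.2). Imputed analysis dates are not named as a source.
- Exclusion from the Per Protocol Set needs a major deviation with a significant impact on the primary endpoint (SAP 6.3).

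Nor should the gap between stop and imputed start be pictured as many months. With a 30-day collection window, the usual affected drug stopped within about 30 days of dosing. Longer gaps could arise mainly for earlier NPDR treatments, which Protocol 6.6.1 captures for 12 months, and for historical anti-VEGF injections. Exclusion criteria 3, 7, 8 and 21 remove many of those.

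**Conclusion.** Wrong as written, and minor. The two partial start-date rules in SAP 8.3.1 give a start that the recorded stop shows to be false, and that start meets one limb of the concomitant definition for a drug taken only before dosing.

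The conclusion needs three conditions together: a partial start that matches the dosing month and year (or the dosing year when the month is also missing), a stop known to be before dosing, and literal application of the rules. The number of such records cannot be derived from the documents and is probably small.

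The effect is on descriptive medication tables. The primary DRSS endpoint does not use these dates. The anti-VEGF and standard-of-care endpoint in SAP 10.2 does read concomitant medication data, but intravitreal anti-VEGF in the 12 months before entry is an exclusion, so an effect there is unlikely. No effect on the Per Protocol Set is shown.

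**What to change.** In SAP 8.3.1, add one condition to both partial-date rules: if the stop date is before the study drug administration date, impute the start as the first of the known month (01 January if only the year is known), and class the medication as prior. Imputing the stop date, as the third rule already does, is an equally good choice.

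In SAP 9.5, state that a medication with a stop date before dosing is prior only.

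Partial stop dates need no new rule. They are already imputed to the end of the month or to 31 December. If that falls on or after dosing, the condition does not apply and the present default remains, which is reasonable because the timing is then unknown.

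The cost is a sentence or two in the SAP and one programming condition. Records without a stop before dosing are unaffected.

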#### 8.3.2. Adverse Event Dates

In the event of a missing/incomplete start or stop date associated with an adverse event, only the treatment-emergence will be imputed using the algorithm below. Dates will not be imputed.

In general, if the missing/incomplete start date is not clearly prior to initiation of treatment, then the AE will be considered at TEAE.

If the AE end date is prior to the initiation of treatment, the AE will not be considered a TEAE.

If the AE end date is on or after the initiation of treatment:

- If the AE start date is completely missing or if the year is missing, then the AE will be considered a TEAE
- For partial AE start dates:
  - Known year, unknown month and day (or known year and day, unknown month)
    - If the year is the same as or later than the year of study drug administration, the AE will be considered a TEAE
    - Otherwise, the AE will not be considered a TEAE
  - Known year and month, unknown day
    - If the month and year are the same as or later than the month and year of the study drug administration, the AE will be considered a TEAE
    - Otherwise, the AE will not be considered a TEAE

#### 8.4. Visit Windows

Safety and efficacy data will be analyzed per study visit. The named visit as recorded in the electronic Case Report Form (eCRF) will be displayed. Pre-specified visit windows are given in [Table 2](#).

Table 2: Visit Windows for Endpoints Collected at All Visits

Visit	Target Study Day	Time Window	Visit Windows for Analysis
Screening	-21 to -5	NA	
Day 1	1	N/A	
Week 4	28	± 5 days	Study Days 2 to 56
Week 12	84	± 5 days	Study Days 57 to 126
Week 24	168	± 5 days	Study Days 127 to 210
Week 36	252	± 5 days	Study Days 211 to 294
Week 48	336	± 5 days	Study Days 295 to 350

This document is confidential.

Visit windows to be used for endpoints not collected at every visit are presented in [Table 3](#), [Table 4](#), and [Table 5](#).

**Table 3: Visit Windows for Wide-field Fluorescein Angiography**

Visit	Target Study Day	Time Window	Visit Windows for Analysis
Screening	-21 to -5	NA	
Week 24	168	± 5 days	Study Days 2 to 210
Week 36	252	± 5 days	Study Days 211 to 294
Week 48	336	± 5 days	Study Days 295 to 350

**Table 4: Visit Windows for Spectral-Domain – Optical Coherence Tomography Angiography (SD-OCTA)**

Visit	Target Study Day	Time Window	Visit Windows for Analysis
Screening	-21 to -5	NA	
Week 24	168	± 5 days	Study Days 2 to 252
Week 48	336	± 5 days	Study Days 253 to 350

**Table 5: Visit Windows for Clinical Laboratory Evaluations and PK**

Visit	Target Study Day	Time Window	Visit Windows for Analysis
Screening (labs only)	-21 to -5	NA	
Day 1 (PK only)	1	NA	
Week 12	84	± 5 days	Study Days 2 to 126
Week 24	168	± 5 days	Study Days 127 to 210
Week 36	252	± 5 days	Study Days 211 to 294
Week 48	336	± 5 days	Study Days 295 to 350

Unscheduled and early termination visits will be associated with a visit according to the visit windows for analysis. Once visits are assigned for analysis, records will be flagged for analysis according to the following rules (in order):

- If a record is available for the scheduled visit, it will be used for analysis.
- If no record is available for the scheduled visit, the available windowed record will be used for analysis.
  - If more than 1 windowed record is available, the record closest to the target study day will be used for analysis.
  - If 2 windowed records are equidistant from the target study day, the windowed record after the target study day will be used.

Electrocardiogram (12-lead) and urine pregnancy data will be summarized at baseline and Week 48 / end of treatment using only nominal visit designators (no visit windows defined).

This document is confidential.

**8.5. Pooling of Centers**

No by-center analyses are planned.

**8.6. Subgroups**

Planned subgroup analyses are detailed in Section 10.1.

**8.7. Multiple Comparisons and Multiplicity**

Not applicable.

**8.8. Adjustment for Covariates**

Secondary efficacy endpoints will include baseline value as a covariate, when applicable.

This document is confidential.

## 9. Demographic, Other Baseline Characteristics and Medication

### 9.1. Subject Disposition and Withdrawals

Subject disposition and withdrawals from the study will be summarized for all subjects in the Screened Set and by treatment arm (for treated subjects) and overall to include the following:

- Number of subjects screened
- Number of screen failure subjects and primary reason for screen failure
- Number of subjects randomized
- Number (%) of randomized subjects in the FAS, PP Set, Safety Set, and PK Set
- Number (%) of subjects completing Week 36
- Number (%) of subjects who discontinued the study at or prior to Week 36 and primary reason for study discontinuation
- Number (%) of subjects completing the study
- Number (%) of subjects who discontinued the study early and primary reason for study discontinuation

A subject is considered to have completed the study if on the eCRF they have a date of completion and have no reason for study discontinuation reported.

